9.2.2 Study time frame

We will use CPRD GOLD and Aurum EHR data from January 1, 2013 through latest available data (currently March 2019).

- Patient identification period: The patient identification period will be restricted to January 1, 2013 through latest available data as shown in the figure above.
- Cohort entry: CAT diagnosis, hospitalization or emergency department admission or primary care visit with an incident VTE event.
- Index date: The date of first rivaroxaban (or any DOAC) or LMWH use according to registered prescription 7-30 days after CAT event (new-user design).
- Pre-index eligibility period: Patients will be required to have at least 12-months of EHR registration prior to the CAT event.
- Post-index eligibility period: There will be no minimum post-index eligibility requirement for patient identification.
- Follow-up period: There will be a minimum of 3 months and maximum 12-months follow-up period. Patients will be followed from the first recording of AC use (7-30 days after CAT event) until the end of eligibility.

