9.3.3 Covariate definition

Patient baseline characteristics such as age, gender, comorbidities, cancer-specific data and comedications will be collected at the index date or from the last recorded value within the baseline period. The presence of characteristics will be assessed from patients' medical and pharmacy data in the baseline period (see Annex 1).

Demographic characteristics

- Sex
- Age
- Race
- Individual DOAC or LMWH used to treat CAT
- Number of days between CAT and first recording of anticoagulation use

Clinical characteristics

- Presence of the following clinical characteristics will be assessed from patients' medical and pharmacy data in the baseline period:
 - **Comorbidities/prior history/risk scores:**
 - Number of days from January 1, 2013 to qualifying CAT diagnosis
 - Cancer type(s) present at CAT diagnosis
 - Metastatic disease at time of CAT diagnosis
 - Active/recent treatment (within 3-months pre- or post-CAT diagnosis)
 - Chemotherapy/immunotherapy
 - Radiation therapy
 - Surgical
 - Initial anticoagulation therapy on day of CAT diagnosis
 - Intracranial bleeding
 - Systemic embolism
 - Deep vein thrombosis
 - Pulmonary embolism
 - Heart failure
 - Hypertension
 - Ischemic stroke/transient ischemic attack
 - Peripheral vascular disease
 - Myocardial infarction
 - Percutaneous coronary intervention
 - Coronary artery bypass grafting
 - Any major bleed

- Major adverse limb events (need for surgical or endovascular revascularization or limb amputation)
- Gastrointestinal bleeding
- Central venous catheter
- Liver disease
- Coagulopathy
- Gastroesophageal reflux disease/heartburn
- Anemia
- Asthma
- Chronic obstructive pulmonary disease
- Sleep apnea
- Smoker
- Alcohol abuse
- Anxiety
- Depression
- Lower extremity paralysis
- Psychosis
- Osteoarthritis
- Diverticulitis
- Crohn's disease or ulcerative colitis
- Active or treated *Helicobacter pylori*
- Hypothyroidism
- Recent major surgery within 12 weeks of index event
- Dementia
- Recent trauma (with 90-days)

- Primary hypercoagulable state (e.g., activated protein C resistance, prothrombin gene mutation, antiphospholipid syndrome, lupus anticoagulant syndrome and other primary thrombophilia (per Read code; ICD-9 or -10 coding provided in Annex 1))
- Prior history of VTE
- Varicose veins
- Chronic venous insufficiency (per Read code or ICD-9 /-10 coding provided in Annex 1)
- Acute coronary syndrome
- Carotid stenosis
- Pneumonia
- Osteoporosis
- Orthopedic surgery

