9.7 Data analysis

Baseline characteristics will be analyzed using descriptive statistics. Categorical data will be reported as percentages and continuous data as medians with accompanying 25%, 75% ranges or means \pm standard deviations (SDs). Descriptive analysis will be performed for each of the three distinct cancer cohorts listed above, namely, (1) the cohort of cancer patients without gastrointestinal and genitourinary cancers, (2) the cohort defined by the ISTH CAT guidelines (in acute CAT patients without a malignant neoplasm associated with a high risk of bleeding) and (3) an all cancer type cohort.

To adjust for potential confounding between the rivaroxaban (or DOAC) and LMWH cohorts, propensity scores will be calculated using a multivariable logistic regression model. The propensity score model will include commonly used variables and accepted risk factors for differential anticoagulation exposure identified at baseline including demographics, comorbidities, laboratory values, vital signs, other clinical observations and outpatient medication use (prescription and over-the-counter). All clinical characteristics listed in section 9.3.3 of this protocol will be included in the propensity score model. Propensity scores will then be used to assign weight to individual patients in the analysis using an overlap weighting approach. Overlap weighting assigns weights to patients that are proportional to their probability of belonging to the opposite treatment cohort. By design, overlap weighting results in the exact balance of all variables included in the propensity score model. This method of adjustment retains all patients in the dataset (unlike propensity score matching) and gives less weight to patients with extreme propensity scores (which is often a concern with inverse probability weighting).

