Propensity scores will be estimated based upon commonly used variables and accepted risk factors for differential anticoagulation exposure identified during the baseline period including demographics, comorbidities, laboratory and vital signs and concurrent outpatient co-medication use. All clinical characteristics listed in section 9.3.3 of this protocol will be included in the propensity score model. Given the retrospective nature of the data analysis, the presence of a comorbid disease diagnosis will be identified based upon the recording of the specific comorbid read codes. Missing data for covariates will occur when an existing co-morbidity or co-medication is not recorded in the database. In such case we will assume that the respective patient did not suffer from the respective co-morbidity/did not use the respective co-

Reference Number: RD-SOP-1214
Supplement Version: 7

medication. Information on time varying variables e.g. BMI and smoking status will assumed to be constant unless a different variable entry is recorded. Whenever meaningful, missing data will be presented in separate categories labelled "not stated" or "unknown". No imputation will be performed for potentially missing outcomes/endpoint data. Separate propensity score models will be fit once for the primary analysis and for each subgroup analysis.

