Cox proportional hazards regression is a method for investigating the effect of variables upon the time a specified event takes to happen. We will fit Cox proportional hazards regression models (with robust estimators) to compare event rates over time for the rivaroxaban (or any DOAC) and LMWH cohorts in the Xarelto SmPC and CAT guidance cancer type cohorts. As propensity score based methods will be assumed to

Reference Number: RD-SOP-1214
Supplement Version: 7

balance key characteristics of the treatment cohorts, the only independent variable that will be included into Cox regression model will be anticoagulant received (rivaroxaban or DOAC or LMWH). Results of Cox regression will be reported as hazard ratios (HRs) with 95% confidence intervals (CIs).

We will use an intention-to-treat approach to analyze the data in which, patients will be evaluated based on the initial anticoagulant prescription registered and will be followed until endpoint occurrence, end-of-database activity, end of data availability or end of designated follow-up time (3-, 6- or 12-months), whichever comes first. Time from treatment initiation to end of follow-up will then be considered the time at risk. On-treatment analysis (patients will be followed until endpoint occurrence, end-of-database activity, end of data availability, end of designated follow-up time (3-, 6- or 12-months), anticoagulant discontinuation or switch, whichever comes first) will be performed as a sensitivity analysis. No adjustments for multiple hypothesis testing will be performed.

Subgroup analyses

Analysis of the recurrent VTE, any clinically-relevant bleeding-related hospitalization and all-cause mortality outcomes among patients prescribed with rivaroxaban and any DOAC (apixaban, dabigatran, edoxaban, rivaroxaban) versus patients prescribed with LMWH patients for acute CAT will be performed stratifying by cancer subtypes (specific subtypes dependent on available sample sizes). To limit the number of analyses performed (and the impact of multiple hypothesis testing), subgroup analyses will only be performed on the primary effectiveness and safety endpoints (recurrent VTE, any clinically-relevant bleeding-related hospitalization and all-cause mortality).

Further descriptive analyses

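### The cancer-treatment covariates in the propensity score can use records up to 61-84 days after the index date, inside the primary outcome window and against the protocol's own baseline rule; the resulting bias has unknown direction and size

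*Protocol*

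**What the plan says.** Protocol 9.3.3 gives a general timing rule: patient characteristics "will be collected at the index date or from the last recorded value within the baseline period". The clinical list repeats it: "Presence of the following clinical characteristics will be assessed from patients' medical and pharmacy data in the baseline period". One item in that list carries its own window, "Active/recent treatment (within 3-months pre- or post-CAT diagnosis", with chemotherapy/immunotherapy, radiation therapy and surgical treatment beneath it.

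Protocol 9.7 says, twice, "All clinical characteristics listed in section 9.3.3 of this protocol will be included in the propensity score model". It also describes the score as built on "accepted risk factors for differential anticoagulation exposure identified during the baseline period". The score then drives the primary analysis: "Propensity scores will then be used to assign weight to individual patients in the analysis using an overlap weighting approach". In the outcome model, "the only independent variable that will be included into Cox regression model will be anticoagulant received".

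Protocol 9.2.2 sets time zero: "Index date: The date of first rivaroxaban (or any DOAC) or LMWH use according to registered prescription 7-30 days after CAT event". It starts follow-up at the same prescription. Protocol 9.3.2 places all three primary outcomes (recurrent VTE, the bleeding composite and all-cause mortality) at 3 months.

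**The concern.** A propensity score should describe patients as they stood when treatment was assigned. Part of the cancer-treatment window lies after that point. To be flagged on a later record, a patient has to live long enough to be treated, and death is itself a primary outcome. The later record may also depend on the anticoagulant or on unmeasured fitness.

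The weighting then acts on this directly. Overlap weights from a logistic model balance the mean of every modelled covariate exactly, as 9.7 notes, so a difference in cancer treatment that arises after index would be forced to zero between the arms. The Cox model contains only the anticoagulant, so all confounding control rests on this score. The 1:1 matching analysis uses propensity scores too and offers no protection, and the subgroup scores are refitted without any different timing rule. Section 9.9 does not mention the issue among the limitations.

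**Working it through.** **Inputs.** Covariate window: 3 months before or after CAT (9.3.3). Index and start of follow-up: day 7 to 30 after CAT (9.2.2). Primary horizon: 3 months (9.3.2). Rates: 11.8 recurrences, 14.4 bleeds and 80.0 deaths per 100 person-years; 5,600 patients; mean follow-up 0.6 years (9.5). Assumption: 3 months = 91 days.

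**The plan's own figures.** 5,600 × 0.6 = 3,360 person-years. Multiplying by the three rates gives 396.5, 483.8 and 2,688 events, against 390, 480 and 2,670 stated. The detectable hazard ratio, exp(−(1.960 + 0.842)/√(D/4)) with D the stated events, two-sided 5%, 80% power and 1:1 allocation, is 0.753, 0.774 and 0.897, against 0.75, 0.77 and 0.89. Section 9.5 therefore reproduces closely. It does not depend on the covariate window and neither supports nor refutes this point.

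**Reach past index.**
- Index on day 30: 91 − 30 = 61 days, and 61/91 = 67% of the primary window.
- Index on day 7: 91 − 7 = 84 days, and 84/91 = 92%.
- If the 3-month horizon is counted from the VTE instead, the flag covers all of the follow-up within it.

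**Deaths inside that reach.** With a constant 80 deaths per 100 person-years, 1 − exp(−0.80 × 61/365.25) = 12.5% and 1 − exp(−0.80 × 84/365.25) = 16.8%. These patients have less time in which to be recorded as treated.

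**Illustration of the bias.** Cohorts of 400,000 (1,500,000 at the VTE rate) were simulated with one measured confounder, a logistic propensity score, overlap weights and an anticoagulant-only Cox model to 91 days. The post-index window was 75 days. The hazard ratio of 0.71 is the more conservative value cited in 9.5. Mechanism strengths are assumptions:
- the DOAC multiplies the rate of starting cancer treatment by exp(±0.4), that is 1.49 or 0.67;
- where cancer treatment affects the event, it multiplies its rate by exp(−0.5) = 0.61;
- unmeasured fitness has log coefficients of +0.7 on starting treatment and −0.7 on the event.

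| Assumed mechanism | Rate | HR, baseline-only score | HR, post-index treatment added |
|---|---|---|---|
| HR 1.0; recording depends only on survival | death | 0.993 | 0.991 |
| HR 0.71; recording depends only on survival | death | 0.713 | 0.723 |
| HR 0.71; recording depends only on survival | VTE | 0.712 | 0.714 |
| HR 0.71; DOAC raises cancer treatment, which lowers the event rate | death | 0.685 | 0.844 |
| HR 0.71; DOAC lowers cancer treatment, which lowers the event rate | death | 0.744 | 0.645 |
| HR 1.0; unmeasured fitness, DOAC raises cancer treatment | death | 1.001 | 1.148 |
| HR 1.0; unmeasured fitness, DOAC lowers cancer treatment | death | 0.995 | 0.879 |

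The comparison is between the last two columns. In the mediated rows the baseline-only value is the total effect, so it differs from 0.71. Three limits apply. Bleeding was not simulated. At the VTE rate only the survival mechanism was run, without competing deaths. The post-index record entered as its own term, whereas the protocol merges it with the earlier period, so patients already flagged by index could not change status; that should dilute the effect.

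**The case against.** The strongest defence is that the general rule governs. The list is headed as baseline data, 9.7 says the same, and the days between CAT and index are both after CAT and legitimately before time zero. A programmer who gave the baseline rule priority would stop at index and no harm would follow. This stands in part: the documents conflict rather than prescribe future data without ambiguity. But a specific window of 3 months after CAT is a more direct instruction than a general heading, and at most 30 of its 91 days can precede index.

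A second defence is that treatment recorded soon after CAT stands in for treatment already planned. That is fair, but cancer type, metastatic disease and treatment up to index remain in the score.

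A third is that this is one item in a long covariate list. That is true and bears on size, not on whether the timing is right.

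A reader might infer that balancing a consequence of the outcome always pulls effects towards the null. The documents do not support that. The only remark on bias towards the null, in 9.9, concerns exposure misclassification, and the simulated bias went both ways and created effects where none existed. A reader might also take 67% to 92% as the share of patients affected. It is calendar reach only: anyone flagged by index is unaffected by later records.

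**Conclusion.** The timing defect holds. As written, the cancer-treatment flags can read up to 61 to 84 days past the index date, overlap about 67% to 92% of the 3-month primary window, and enter the score on which all confounding control depends. That conflicts with the protocol's own baseline rule in 9.3.3 and 9.7. Confidence in this part is high, because it rests on stated dates and the 91-day convention.

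The direction and size of the bias are unknown. Under assumed mechanisms the shift is negligible at the VTE rate when recording depends only on survival, and small at the death rate (0.713 to 0.723). It becomes material for mortality when the anticoagulant also affects cancer treatment, and it can then go towards the null, away from it, or produce an apparent effect from none. The protocol gives no figure that would choose between these cases, so the bias cannot be dismissed as conservative. The conflict should be resolved before the score is programmed.

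**What to change.** In 9.3.3, define the window for chemotherapy/immunotherapy, radiation and surgery as running from 3 months before CAT diagnosis up to and including the index date. Name that date as the first recorded DOAC or LMWH prescription, because 9.1 uses the term index date for the CAT event. In 9.7, state that every propensity-score covariate uses only records dated on or before that date. Cancer treatment after index may be described but should not enter the score.

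The look-back should keep its start at 3 months before CAT. Counting 3 months back from index would also be free of future data, but with index on day 30 it would drop valid records older than 91 − 30 = 61 days before CAT.

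The cost is about one line in each section, and no figure in 9.5 changes. There are two downsides. Treatment planned but not yet recorded at index is not captured. The definition may also differ from the OSCAR-US protocol on which this one is based (section 7), so it should be aligned across the programme before the planned meta-analysis.

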9.4 Data sources

CPRD collects fully-coded patient electronic health records from GP practices using the Vision® (CPRD GOLD) or EMIS® (CPRD Aurum) software systems. Due to some differences in structure and clinical coding in these two systems, these data are provided as two separate primary care databases that can be pooled. The CPRD GOLD is a computerized primary care database containing anonymized records for more than 5.4 million active patients who are registered with participating primary care practices in the UK, which represents approximately 8% of the UK population. It contains diagnostic and prescribing information recorded by GPs as part of their routine clinical practice in the UK, also information about consultant referrals and hospitalizations, laboratory test results and diagnoses procedures (<http://www.cprd.com/intro.asp>). The CPRD also includes information recorded by GPs on patient demographics, lifestyle factors and detailed information on prescriptions written by the PCP.

The CPRD Aurum database contains longitudinal routinely-collected electronic health records from primary care practices in England. The database captures information on: Demographic characteristics, Diagnoses

and symptoms, prescriptions, tests, referrals to hospital and specialist care. The key strengths of CPRD Aurum are its size and coverage (complementing CPRD GOLD), longitudinal follow-up, representativeness, and standard linkages to national secondary care databases like Hospital Episode Statistics (HES) as well as deprivation and death registration data [6, 7].

CPRD data are linkable, at least partially, with other health care data sets (e.g., hospitalization -HES and national mortality data). Briefly, Hospital Episode Statistics (HES) are data collected from National Health Service (NHS) hospitals in England by the Secondary Uses Services (SUS), a programme that supports secondary care in the NHS. HES data include details of all hospital care funded by the NHS in England. It contains: admitted patient care data from 1997 onwards, outpatient attendance data from 2003 onwards and accident and Emergency (A&E) data from 2007 onwards. The full HES dataset contains more than 400 fields, although in most cases many of these are not completed by the hospital, either because they are not applicable or recording is not mandatory.

For the present study we will request linkage to different sources to obtain valid and complete information:

- 1.- HES Admitted Patient Care (HES APC) : Complete hospital episode information (admission and discharge dates, diagnoses (identifying primary diagnosis), specialists seen under and procedures undertaken) for each linked patient with a hospitalization record. This is necessary if we do not want to miss any study hospitalized outcome.
- 2.- HES Accident and Emergency (HES A&E) data of patients attending hospitals that may be further be hospitalized. From all information recorded we are specially interest in: A&E diagnosis.
- 3.- Death Registration data contains data from the Office for National Statistics (ONS) and includes information on the official date and causes of death (using ICD codes). This is important to ascertain potential outcomes that may not be in previous sources, but can identify patients dying from the outcome we are studying.

We will request approval to obtain the three linked data sources (HES APC, HES A&E, ONS Death registration) to ascertain all potential study outcome of interest resulting in a hospitalization or being the cause of death. On the other hand we will not request The HES Outpatient (HES OP), as data completeness is an issue in some OP fields and outpatient information may not add relevant clinical information of use for our outcome definitions.

Patients registered in CPRD database are age, sex, and geographically representative of the UK population, and has been extensively validated for use in epidemiological studies [5]. Updated, valid, linked data are available through the CPRD Division of the UK Medicines and Health Care Products Regulatory Agency

Research at the CPRD requires approval from the CPRD Independent Scientific Advisory Committee (ISAC).

The Read classification is used to code specific diagnoses [11, 12] and a drug dictionary based on data from the Gemscript classification is used to record prescriptions [13]. Currently, active patients included in CPRD-GOLD are over 3 million and the corresponding number in Aurum approximates 13 million.

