9.3.2 Outcomes definition

The study outcomes will be defined based on Read codes and ICD-9/10-CM diagnosis and procedure codes or laboratory, vital sign and other patient observation results.

Algorithms for the definition of recurrent VTE and of the bleeding events have previously been developed and refined using all information available in CPRD, HES and Office of National Statistics ONS [4, 8].

A random sample of identified potential VTE recurrences and significant bleeding events will be manually reviewed by utilizing patient summaries/profiles including HES APC, HES Outpatient, ONS death registration data (DRD) and PCP recorded symptoms, signs, laboratory tests, diagnostic and therapeutic procedures, medication use, discharge diagnoses, and cause of death to confirm the that outcomes have been appropriately identified.

Primary outcomes

- The risk of recurrent VTE at 3-months
- Composite of any major bleeding or clinically-relevant non-major bleeding-related hospitalization (per the ISTH criteria [9, 10] for identification of bleeding-associated hospitalizations) at 3-months
- All-cause mortality at 3-months

Secondary outcomes

- Recurrent VTE at 6- and 12-months post-index VTE

- Composite of any major or clinically-relevant nonmajor bleeding-related hospitalization at 6- and 12-months post-index VTE, including:
 - Intracranial hemorrhage (ICH)
 - Critical organ bleeding (e.g., intracranial, intraspinal, intraocular, retroperitoneal, intraarticular or pericardial bleeding or intramuscular with compartment syndrome)
 - Extracranial bleeding-related hospitalizations (including trauma-related)
- Composite of any major bleeding or clinically-relevant non-major bleeding-related hospitalization (per the ISTH criteria [9, 10] for identification of bleeding-associated hospitalizations) at 6 and 12-months
- Intracranial hemorrhage (ICH), critical organ bleeding and extracranial bleeding-related hospitalizations as separate outcomes
- All-cause mortality at 6- and 12-months
- Incidence rates of recurrent VTE, any clinically-relevant bleeding-related hospitalization and all cause-mortality in rivaroxaban, DOAC and LMWH patients experiencing CAT regardless of the bleeding risk associated with cancer type
- Duration of anticoagulation treatment and rivaroxaban, DOAC and LMWH discontinuation rates at 3-, 6-, 12-months and all available follow-up

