Propensity score matching operates by taking each treated study participant and finding the closest propensity score match among controls within a calliper (or bound). Conventional IPTW assigns a weight of $1/PS$ for treated and $1/(1 - PS)$ for untreated patients, allowing individuals with underrepresented characteristics to count more in the analysis. IPTW can produce inflated variance estimates which can be addressed through a simple stabilization of weights (multiplying propensity scores of each participant by the relative proportion of the specific cohort makes up of the total study population). In observational data, in which the initial differences in treatment groups may be large, these methods can modify the target population, fail to achieve good balance or substantially worsen precision. Overlap weighting assigns weights to each patient that are proportional to the probability of that patient belonging to the opposite treatment group. Specifically, treated patients are weighted by the probability of not receiving treatment ($1 - PS$) and untreated patients are weighted by the probability of receiving the treatment (PS). These weights are smaller for extreme PS values so that outliers who are nearly always treated (PS near 1) or never treated (PS near 0) do not dominate results and worsen precision, as occurs with IPTW. These outliers contribute relatively less to the result, while patients whose characteristics are compatible with either treatment contribute relatively more. The resulting target population mimics the characteristics. Overlap weighting also leads to exact balance on the mean of every measured covariate when the PS is estimated by a logistic regression. Like all PS-based methods, overlap weighting cannot adjust for patient characteristics that are not measured and included in the model for the PS. When initial imbalances in patient characteristics between treatment groups are modest, overlap weighting yields similar results to IPTW. The advantages of overlap weighting are greatest when comparator groups are initially very different. To test the robustness of our conclusions to various methods for confounding adjustment, we will also perform a number of sensitivity analyses e.g. *1:1* matching based on propensity scores.

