9.9 Limitations of the research methods

As with any secondary data source, CPRD databases have limitations. Key limitations include:

- Misclassification of exposures can negatively impact the internal validity of observational studies.
- In general, in database analyses, the absence of information is taken as an indication of absence of the condition. Missing values may occur in a small proportion for some lifestyle habits. In this case, individuals with missing values will be kept in the analysis and a separate category will be created for missing values of that variable.
- DOAC prescriptions started in-hospital or events in the immediate post-discharge period are likely to be missed in the CPRD UK databases. This might induce some exposure misclassification that we expect to be non-differential between patients prescribed OACS and those prescribed LWMH. This might introduce some bias towards the null in study estimates. While bias towards the null is generally considered as conservative in effectiveness analyses, it is considered as anticonservative in safety analyses (tends to conclude treatment strategies are similar even if they are not). This will be taken into account when interpreting study results.
- In database analyses where randomization is not possible, such PS based methods such as weighting or matching serve to harmonize comparison groups with respect to patient characteristics. However, residual confounding caused by e.g. unmeasured factors, missing data, miscoding or tactical coding issues, etc. may be present.

Reference Number: RD-SOP-1214
Supplement Version: 7

- CPRD captures prescriptions recorded by the PCP, but do not capture if a patient filled their prescription and/or took it. The study is thus designed as an intention-to-treat approach, subsequent recording of anticoagulants will be evaluated to estimate time on anticoagulation treatment and discontinuation rates as exploratory outcomes.
- No adjustment for multiplicity hypothesis testing will be performed.

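### Area deprivation is named as an available linkage of CPRD Aurum but is neither requested nor adjusted for, so some social confounding of the DOAC versus LMWH comparison, mainly for 3-month mortality, may remain

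*Protocol*

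**What the plan says.** **Availability.** Among the strengths of CPRD Aurum, section 9.4 lists "standard linkages to national secondary care databases like Hospital Episode Statistics (HES) as well as deprivation and death registration data". The statement is about Aurum and not about GOLD. Aurum is the larger source: 9.4 gives it about 13 million active patients. For GOLD it gives over 3 million in one place and more than 5.4 million in another.

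**Request.** The same section then says "We will request approval to obtain the three linked data sources (HES APC, HES A&E, ONS Death registration". The stated purpose is to find outcomes that lead to hospital admission or death. A reason is given for leaving out HES Outpatient. None is given for leaving out deprivation.

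**Covariates.** Section 9.3.3 opens with "Patient baseline characteristics such as age, gender, comorbidities, cancer-specific data and comedications will be collected at the index date". Its demographic items are sex, age, race, the individual drug and the days from CAT to the first anticoagulant record. No item in the section measures deprivation, income, education or area.

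**Adjustment.** Section 9.7 states "All clinical characteristics listed in section 9.3.3 of this protocol will be included in the propensity score model", and for the outcome model "the only independent variable that will be included into Cox regression model will be anticoagulant received".

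**Outcome.** Section 9.3.2 lists "All-cause mortality at 3-months" as a primary outcome.

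**The concern.** The linkages were chosen by their use for outcomes, and the protocol does not discuss whether a linkage is also needed to measure confounders. Deprivation could plausibly relate to survival in cancer patients, through late presentation, smoking, comorbidity and access to care. It could also relate to which anticoagulant a patient is prescribed, for example through local prescribing habits. These links are assumptions, because the protocol gives no data on them. If both hold, part of the mortality difference between DOAC and LMWH users would be social rather than pharmacological. Bleeding could be affected to a lesser degree.

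The point belongs at protocol stage. A later analysis plan can change a model, but it cannot adjust for a data set that was never requested. The planned sensitivity analyses in 9.7 (1:1 matching, competing risks, on-treatment follow-up, hospital-treated VTE only) add no socioeconomic covariate, so they share the gap.

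**Working it through.** **1. The protocol's own figures.** Section 9.5 gives 5,600 patients, a mean follow-up of 0.6 years and 80.0 deaths per 100 person-years.

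- Person-years: 5,600 × 0.6 = 3,360.
- Deaths: 3,360 × 0.80 = 2,688, against the stated 2,670.
- Detectable HR by Schoenfeld's formula, two-sided 5% (sidedness is not stated), 80% power: exp(−(1.960 + 0.842) / √(D·p·(1−p))). With D = 2,670 and equal groups this is 0.897. With a 1:2 split it is 0.891. The protocol states 0.89.

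The figures reproduce, and they do not depend on the present point. The 0.89 rests on deaths over the first year after CAT.

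**2. Bias from an omitted two-level factor.** No inputs are in the protocol, so all of these are assumed. Let g be the mortality HR for more-deprived patients, p1 their share among DOAC users and p0 their share among LMWH users. With no true drug effect the apparent HR is approximately (1 + (g−1)·p1) / (1 + (g−1)·p0).

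| g | p1 vs p0 | Apparent HR | If shares are reversed |
|---|---|---|---|
| 1.2 | 35% vs 40% | 1.07/1.08 = 0.991 | 1.009 |
| 1.2 | 35% vs 45% | 1.07/1.09 = 0.982 | 1.019 |
| 1.4 | 35% vs 40% | 1.14/1.16 = 0.983 | 1.018 |
| 1.4 | 35% vs 45% | 1.14/1.18 = 0.966 | 1.035 |

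These values give no credit for the listed covariates that correlate with deprivation. They also do not bound the bias, because stronger inputs give more. With g = 1.5 and 15% vs 25% the result is 1.075/1.125 = 0.956. With g = 2.0 and 10% vs 30% it is 1.10/1.30 = 0.846.

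**3. Effect on false-positive error.** At a constant hazard of 0.80 per year (an assumption), deaths by 3 months are 5,600 × (1 − exp(−0.80 × 0.25)) = about 1,015. With equal groups, the HR needed for two-sided significance is exp(−1.96/√(1,015/4)) = 0.884. For the first-year count of 2,670 it is 0.927. With s = |ln(apparent HR)| × √(D/4), the chance of a significant result under no true effect is 1 − Φ(1.96 − s) + Φ(−1.96 − s):

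| Apparent HR | 3 months (1,015 deaths) | 12 months (2,670 deaths) |
|---|---|---|
| 0.99 | 5.3% | 5.8% |
| 0.98 | 6.2% | 8.2% |
| 0.97 | 7.7% | 12.3% |

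Both columns use all 5,600 patients. The comparative cohorts exclude cancers with a high bleeding risk, so they hold fewer deaths and the inflation would be smaller.

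**The case against.** **The arms are not shown to differ socially.** A reader might infer that social differences are present and will bias the primary mortality result, perhaps in favour of DOACs. The protocol does not support that. Nothing in it says that deprivation relates to drug choice, and nothing points to a direction. This objection stands, and the point is limited to confounding that may remain.

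**Much of the pathway is already covered.** Section 9.3.3 includes smoking, alcohol abuse, BMI, COPD, depression, psychosis, frailty, number of hospitalizations, race, cancer type, metastatic disease, cancer treatment and calendar time. Of the pathways named above, only access to care has no direct counterpart. This also stands. It reduces the likely size but does not show that nothing is left.

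**The limitation is disclosed.** Section 9.7 says "overlap weighting cannot adjust for patient characteristics that are not measured and included in the model for the PS", and 9.9 adds "residual confounding caused by e.g. unmeasured factors, missing data, miscoding or tactical coding issues, etc. may be present". These are general statements. They do not explain why a factor that 9.4 itself names as available is left unmeasured.

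**The covariate list may be a minimum.** Section 9.7 also speaks of commonly used variables and accepted risk factors, so items could be added later. That is fair, but the request for three linkages is what limits the data.

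**Harmonisation.** Section 7 aims for common definitions across the US, UK and Swedish studies. A UK area index is specific to one country. This is a real but modest drawback, since nothing in the protocol bars a study-specific covariate.

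**Conclusion.** The gap is real and the remedy is inexpensive, but the consequence is a possibility and not a demonstrated bias. Deprivation is named as linkable for Aurum, is not requested, and appears in neither the covariate list nor the outcome model. No passage contradicts another, so this is an avoidable omission and not an error.

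Under the assumed inputs the spurious HR is about 0.97 to 0.99, or about 1.01 to 1.04 in the other direction. At 3 months that would move a nominal 5% error rate to between about 5% and 8%.

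Two stronger readings should be avoided. The first sets the bias against the HR of 0.89 in 9.5 as if that were the benchmark for the primary outcome. That figure is for 12 months, and the primary outcome is at 3 months. The second treats the linkage as available for the whole study. Section 9.4 names it for Aurum only, while the study pools Aurum with GOLD.

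**What to change.** - **9.4:** add the area-level deprivation linkage to the three data sources to be requested.
- **9.3.3:** add deprivation quintile to the demographic characteristics, with an unknown category for unlinked patients (for example in GOLD, if the linkage is not available there). This fits the handling of missing covariates already set out in 9.7 and 9.9.
- **9.7:** include it in each propensity score model, including those for subgroups and for the 1:1 matching, and show it in the baseline and balance tables.

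If the linkage is not pursued, 9.4 should say why, 9.9 should name deprivation as an unmeasured factor, and a quantitative bias analysis for mortality should be planned.

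**Cost:** one more linked data set to request and one more categorical covariate. No new patients or procedures are needed. The protocol gives no fee or approval time for the extra linkage. The covariate would be UK-specific, so the report should note for the planned OSCAR meta-analysis that the UK adjustment set differs by this item.
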